## 7.2 Clinical Laboratory Evaluation

Central laboratory data are transferred electronically by Covance. The Data Transfer Specification document provides a detailed description of the content and format of the laboratory datasets. Both conventional and SI units are provided and will be summarized in separate tables and listings. The eGFR values will be calculated and included in the tables and listings for clinical chemistry parameters.

Results from local laboratories are entered into the CRF by the site; these will not be included in summary tabulations but will be included in the data listings together with the corresponding normal ranges. Values for local laboratory parameters will be converted to the corresponding alternative units, either conventional or SI, depending on how reported.

For the summary tabulations of laboratory results, Baseline is defined as the last non-missing value prior to first dose of study drug in 020. Laboratory tests obtained on the date of the first dose will be assigned to pre-treatment. For each analyte, Baseline values will be restricted to those subjects in the safety population for whom there is at least one post-Baseline value (either overall or for the corresponding target visit). Any lab result 14 or more days after the last dose will be considered post-treatment.

Visit windows are used when results are presented by target visit (see [Appendix A](#)). For each analyte, if a subject has multiple values within a visit window, the “worst” value as defined in [Appendix D](#) will be used for that visit window summary.

Results of all continuous laboratory parameters will be summarized using descriptive statistics at baseline and at each post-baseline target visit; the last available on-treatment value and post-treatment results will also be summarized. The baseline data may come from the prior study, if not repeated in 020. For each subsequent target visit, changes from baseline will also be summarized by the number and percentage of subjects and the mean, median, SD, minimum, and maximum values for continuous laboratory parameters. These will also be prepared for subjects categorized by diagnosis and AChEI/Memantine use.

Box and whisker plots will be presented for selected parameters including hemoglobin, reticulocytes (%), neutrophils, and liver function tests. Other parameters may be identified during data review.

Thresholds for potentially clinically significant (PCS) laboratory abnormalities are defined in [Appendix B](#) for selected parameters. When there are thresholds provided for low and high values, they will be handled separately. Summaries will include the number and percent of subjects with treatment-emergent PCS values, restricted to those subjects in

whom the values represent a post-baseline worsening (PCST); the number meeting criteria at baseline will also be summarized. A PCST is defined as any PCS event that happened at any post-baseline visit and has a value more out of range than the value for a particular test at baseline (see [Appendix D](#) for directionality of worsening).

Listings of laboratory parameter results will be presented. Listings will include all laboratory flags provided by the central laboratory in the data transfer as well as flags for those that meet criteria for being PCS (whether or not a study-emergent worsening); additionally, results evaluated by the investigator as abnormal/clinically significant will be flagged in the listing. A separate listing for samples that could not be analyzed and the corresponding comments will be provided.

Separate listings for each hematology and chemistry parameter will include only subjects with treatment-emergent PCS values and, for these subjects, all laboratory results for the parameter meeting PCS criteria and related parameters (e.g., ALT, AST, bilirubin, neutrophils, WBC, etc.) will be provided.

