## **4. GENERAL ANALYSIS CONSIDERATIONS**

The Safety population will include all subjects who take at least one dose of study drug. All analyses described in this SAP will be based on the Safety Population. All subjects entering the study, even if not known to have taken a dose, will be accounted for in a listing.

The statistical analyses will be reported using summary tables, figures, and data listings. Continuous variables will be summarized with means, standard deviations, medians, minimums, and maximums. Categorical variables will be summarized by counts and by percentage of subjects in corresponding categories.

For purposes of calculations of change from baseline, Baseline (Visit 1) for the open-label study will be used. Depending on the parameter, the data may have been acquired during the double-blind study of prior participation.

Summary tables will present results by diagnosis (AD or bvFTD) and an “All Subjects” column.

Individual subject data obtained from the CRFs (including mapped data), central clinical laboratory (local laboratory results are entered on the CRFs), and any derived data will be presented by subject in data listings. Listings will include relative study day, where negative values will indicate visits prior to first dose of study drug in 020, and any data collected after discontinuation of study drug will be flagged as follow-up. All data captured on the CRF, including specific descriptions of ‘other’ and comments fields, will be included on the listings. Listings will be sorted by subject number.

All analyses and tabulations will be performed using SAS® Version 9.4 or higher. Tables, listings, and figures will be presented in RTF format. Upon completion, all SAS® programs will be validated by an independent programmer. In addition, all program output will undergo a senior level statistical review. The validation process will be used to confirm that statistically valid methods have been implemented and that all data manipulations and calculations are accurate. Checks will be made to ensure accuracy, consistency with this plan, consistency within tables, and consistency between tables and corresponding data listings. Upon completion of validation and quality review procedures, all documentation will be collected and filed by the project statistician or designee.

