#### **4.4 Visit Windows**

Since study visits do not always take place exactly as scheduled in the protocol, it is necessary to assign the actual observation times to “analysis visit windows” for analysis purposes. Post-baseline visit windows for each target visit are defined in [Appendix A](#), and will be applied to all measurements. For each summary and value if there are multiple values within a visit window, the “worst” value as defined in [Appendix D](#) will be used for that visit window summary. These visit windows will be applied to all visits, including scheduled, unscheduled, and early termination visits.

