## **7. SAFETY ANALYSES**

### **7.1 Adverse Events**

There are two CRFs contributing adverse event data.

- **Prior Study – Adverse Events CRF:** All adverse events as recorded during prior studies 005, 007 and 015 will be automatically uploaded to the Prior Study – Adverse Events CRF and adverse events recorded during the 008 study will be recopied from the 008 records by the site to the Prior Study – Adverse Events CRF. The only field that can be modified by the site is the OLEX end date as applicable. Additionally there is a comment field where text can be entered by site.
- **Adverse Event CRF:** New adverse events or changes to an existing adverse event will be recorded on the Adverse Event CRF.

Adverse events will be coded to SOC and PT using MedDRA (version 16.0). The coding process is described in the Data Management Plan.

AEs are grouped as follows and source(s) of data identified:

1. **Prior AEs:** AEs that were ongoing at the end of the prior study but that resolved before Day 1 of dosing in 020 or that started and resolved during the gap between studies. The source would be both the Prior Study – Adverse Events CRF and the (020) Adverse Event CRF.
2. **Pre-existing AEs:** AEs that were ongoing on Day 1 of dosing in 020 - source is the Prior Study – Adverse Events CRF. The source would be both the Prior Study – Adverse Events CRF and the (020) Adverse Event CRF.

3. Study-emergent AEs: AEs that started on or after Day 1 of dosing in 020, excluding post-treatment AEs (defined in #5 below). The source would be the (020) Adverse Event CRF.
4. All AEs: Whether pre-existing or study-emergent (merge of AEs that were ongoing on Day 1 of dosing) excluding post-treatment AEs. Sources are the Prior Study – Adverse Events CRF and the (020) Adverse Event CRF (note, this is a merge of #2 and 3 above *only*).
5. Post-treatment AEs: The study-emergent AEs (3# above) that have an onset more than 14 days after the last dose of study drug or that worsen in intensity or treatment attribution following discontinuation more than 14 days after the last dose of study drug.

The tabular summaries will be provided for AEs, with the number and percentage of subjects reporting each type of event. If a subject reports the same preferred term more than once, it is counted only once within that category. Further, for a given tabulation, the preferred term will only be counted once at its worst severity and strongest relationship to treatment.

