**APPENDICES**

**Appendix A: Post-Dose Visit Windows**

Visit windows are defined in the following table. Unscheduled and early termination visits are included in the windowing algorithm.

Target Visit	Visit Window Time Interval (Study Day*)	Scheduled Day
Baseline	< 2	NA
Week 2	2 to 53	15
Week 13	54 to 137	92
Week 26	138 to 228	183
Week 39	229 to 319	274
Week 52	320 to 410	365
Week 65	411 to 501	456
Week 78	502 to 591	546
Week 91	592 to 683	637
Week 104	> 683	729
Follow-up	First post-treatment value at least 14 days after last dose	

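### The treatment-emergent PCS definition for laboratory tests and vital signs has no on-treatment limit, so off-drug follow-up values can enter the pooled counts and PCS listings

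*SAP*

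**What the plan says.** SAP 7.2 defines the treatment-emergent class for laboratory results: "A PCST is defined as any PCS event that happened at any post-baseline visit", provided the value is further out of range than at baseline. SAP 7.3 repeats the definition for vital signs. The laboratory shell (Table 14.3.3.3.1) has pooled rows for any post-baseline PCS value and any post-baseline worsening, and its footnote explains treatment-emergent only as further out of range. The vital-sign shell (Table 14.3.4.1.3.1) has a pooled row for any post-baseline visit. The programming notes to both shells ask separately for the last available on-treatment value.

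Other parts of the SAP do draw a line at the end of treatment:

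- **Laboratory summaries, SAP 7.2:** "Any lab result 14 or more days after the last dose will be considered post-treatment". For the continuous parameters, "the last available on-treatment value and post-treatment results will also be summarized", named apart from the post-baseline target visits.
- **Visit windows, SAP Appendix A:** a Follow-up row defined as "First post-treatment value at least 14 days after last dose". SAP 4.4 applies the windows to all measurements and keeps the worst value where several fall in one window.
- **Adverse events, SAP 7.1:** study-emergent events are "AEs that started on or after Day 1 of dosing in 020, excluding post-treatment AEs", the latter being those with onset more than 14 days after the last dose.
- **Listings, SAP 4:** "any data collected after discontinuation of study drug will be flagged as follow-up".

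The protocol schedules the follow-up visit for everyone who stops LMTM (Section 4.1), at 28 ± 14 days after the last dose (Appendix A). Laboratory tests, vital signs and weight are repeated there (Sections 7.3, 7.4 and 7.4.3).

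**The concern.** The study's analytic objective is long-term safety and tolerability on LMTM. A table of treatment-emergent abnormalities will be read as describing what appeared under treatment. As defined, a subject with no qualifying value on drug and one at the off-drug visit is counted in the pooled row. PCST status also decides who enters the separate by-parameter listings, so those can gain subjects in the same way.

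An adverse event with onset at that same visit, if more than 14 days after the last dose, would leave the study-emergent class and go to its own table. The two halves of the safety report would then classify one off-drug finding differently. In the laboratory section the SAP's own sentences point both ways, so two programmers could follow the text faithfully and produce different counts.

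**Working it through.** The plan states no PCS rate, sample size or precision target here, so there is no figure of its own to reproduce. The check compares the rules and then the windows.

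**1. Does a follow-up value meet both rules?** The visit falls 28 − 14 = 14 to 28 + 14 = 42 days after the last dose. Every on-schedule follow-up laboratory result is therefore at least 14 days off drug, which is post-treatment under SAP 7.2. It is also at a post-baseline visit, so it is eligible for PCST. SAP 7.2 does not say which rule governs. SAP 7.3 has no corresponding sentence for vital signs; the 14-day cut reaches them only through the Follow-up row of Appendix A, and that row assigns a value to a visit without restricting PCST.

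**2. Does post-baseline mean on-treatment in this SAP?** No. The shells ask for the last available on-treatment value as a separate item, and Appendix A includes Follow-up among the target visits.

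**3. Can a follow-up value also sit in a study-day window?** The windows run from Day 2 without a gap and the last is open-ended (after Day 683), so every off-drug value also satisfies one of them. With the last dose on the scheduled visit day:

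| Last dose | Follow-up range (+14 to +42) | Window containing the last dose |
|---|---|---|
| Day 92 | 106–134 | Week 13: 54–137 |
| Day 183 | 197–225 | Week 26: 138–228 |
| Day 274 | 288–316 | Week 39: 229–319 |
| Day 365 | 379–407 | Week 52: 320–410 |

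In each row the whole follow-up range lies inside the window that holds the last on-drug visit. Appendix A does not say that Follow-up takes precedence. If it does not, the worst-value rule chooses between the on-drug and off-drug value. For weight, SAP Appendix D makes the worst value the greatest loss from baseline, so an off-drug weight could stand for Week 52 and be tested against the 7% and 10% criteria of SAP Appendix C.

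**4. Direction and relative size.** Adding a visit to an any-visit count cannot lower it. For illustration only, assume a constant, independent chance q of a qualifying value per visit, with k on-drug visits and one follow-up. The proportion flagged is 1 − (1 − q)^k without the follow-up and 1 − (1 − q)^(k+1) with it. The share of flagged subjects first seen at follow-up is the difference divided by the second figure.

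| k | q = 0.5% | q = 5% |
|---|---|---|
| 1 (early stop) | 0.50% → 1.00%, share 49.9% | 5.00% → 9.75%, share 48.7% |
| 5 (Visits 2–6) | 2.48% → 2.96%, share 16.5% | 22.62% → 26.49%, share 14.6% |
| 9 (Visits 2–10) | 4.41% → 4.89%, share 9.8% | 36.98% → 40.13%, share 7.9% |

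The values of q are assumptions with no source in the documents. Repeated values within a subject are likely to be correlated, in which case one more visit adds less than this. What the table supports is the pattern: the relative effect shrinks as on-drug visits accumulate.

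**The case against.** The case for leaving the text alone has several sound parts.

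- A reader might infer that the SAP plainly reports off-drug laboratory abnormalities as arising on treatment. It does not. SAP 7.2 classes results from 14 days onward as post-treatment for the summary tabulations, so the fault for laboratory tests is an unresolved conflict.
- A reader might also infer that vital signs have no post-treatment cut at all. SAP 7.3 uses the Appendix A windows, so the Follow-up row does reach them.
- The ordinary reading of Appendix A is that a follow-up value goes to Follow-up. The Week 52 overlap arises only because precedence is unstated; it is not shown that values will be misassigned.
- Treatment-emergent does not always mean on drug here. Protocol 9.6.1 and the note to SAP Table 14.3.2.15.1 treat post-treatment AEs as a subset of TEAEs, and the pooled PCS rows are openly labelled post-baseline.
- Off-drug data are flagged in listings, Follow-up is a target visit of its own, and post-treatment AEs are tabulated. The analysis is single-arm and descriptive, and counting too many abnormalities errs on the cautious side.

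All of this narrows the point, and the by-visit display and listing flags are real safeguards. They do not correct the pooled rows or the rule for entry to the PCS listings. If off-drug values are meant to be included, the SAP should say so and reconcile that with its own 14-day rule.

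**Conclusion.** The point holds as a defect of definition. PCST has no on-treatment limit in SAP 7.2 or 7.3. For laboratory tests this conflicts with the 14-day rule in the same section; for vital signs no rule restricts PCST. The missing precedence rule in Appendix A adds a second route by which an off-drug value can be reported as an on-treatment visit. The consequence is confined to the pooled any-post-baseline rows, entry to the PCS listings and, if Follow-up is not given precedence, the study-day visit summaries.

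The size is unknown because the documents give no PCS rates, and the figures in the working must not be read as estimates. The direction for the counts is upward, and the relative effect is larger for subjects with few on-drug visits. It applies only to subjects who stop LMTM and attend follow-up; those who continue into a further extension have no such visit in between.

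One further inference should be resisted: that these abnormalities began after the drug was stopped. First seen off drug is not the same as begun off drug. A weight change in particular may have built up largely during treatment. The definition simply does not separate the two periods.

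**What to change.** 1. In SAP 7.2 and 7.3, define PCST on post-baseline values obtained less than 14 days after the last dose.
2. In SAP Appendix A, state that values 14 or more days after the last dose are assigned only to post-treatment/Follow-up and never to a study-day window, for laboratory tests, vital signs and ECG.
3. In Tables 14.3.3.3.1 and 14.3.4.1.3.1 and their repeats in non-AChEI/memantine users, report post-treatment PCS values in a separate row.

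This uses the SAP's existing laboratory cut and needs no new data: a few sentences of text and one extra row per criterion. The downside is that the pooled PCST counts no longer include abnormalities first seen off drug. Those stay visible in the added row.

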7.3 Clinical Laboratory Tests

Scheduled blood samples for hematology and chemistry panels will be obtained at each visit during the study, including Baseline (if not available within the prior 42 days), after 2 weeks, and approximately every 13 weeks (relative to Baseline) thereafter (or upon early termination). Laboratory testing will be repeated at the 4-week post-treatment follow-up visit if applicable.

A trained and authorized person will collect blood samples from the subject by venipuncture from a suitable vein.

Kits with supplies for the collection of blood samples will be provided to each study site before the study initiation visit. The kits will be labeled to identify the clinical study, and will include specimen labels, pre-printed laboratory requisition forms, all supplies needed for specimen collection and shipping, instructions for collection and preparation of specimens, and pre-printed forms to expedite shipment.

A protocol-specific laboratory manual will be provided to each study site. The laboratory manual will include contact details, lists of the contents of collection kits, shipment schedule of collection kits, and detailed guidelines and recommendations for completing laboratory requisition and for specimen collection, preparation, storage, and transportation.

A central laboratory will process all scheduled laboratory blood samples unless otherwise noted. Data will be transferred electronically for inclusion in the database. Investigators are to enter the results of any testing performed at local laboratories (and the corresponding normal ranges) into the eCRF.

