The first on-treatment visit will occur approximately 2 weeks after Visit 1 (designated Visit 2) for the initial post-treatment safety assessment. During the first year, post-Baseline study visits will occur at approximately 2 weeks (Visit 2), 13 weeks (Visit 3), 26 weeks (Visit 4), 39 weeks (Visit 5), and 52 weeks (Visit 6) after Baseline. Required assessments will be performed at all visits as described in the Schedule of Assessments in Section 3.1. Caregivers will be contacted by telephone at the mid-point between Visits 2 and 3; they will also be asked to contact the investigator in response to any safety concern. An unscheduled visit will be arranged to assess the subject as needed.

Continued participation will be re-evaluated approximately every 12 months on the basis of safety, tolerability, and continued benefit as judged by the investigator. Subjects deemed eligible for continued treatment (and their caregivers) must provide informed consent for re-enrollment. Subjects for whom consent is not provided consistent with national requirements and IRB/EC approval will be discontinued.

For subjects who cease to take LMTM, a post-treatment follow-up visit 4 weeks after the last dose of study drug is to be scheduled, regardless of the reason for discontinuation. Subjects who fail to complete the initial 12-month extension period will not be eligible to continue to receive treatment during any subsequent extension period.

A schematic representation of the first 12 months of the study is provided in Table 3-1.

Table 3-1 Schematic Representation of Study (First 12 Months)								
	1 st Dose						Last Dose	Follow-up (4 wks after last dose)
Visit	1	2	(T)*	3	4	5	6	-
Week	0	2	5	13	26	39	52	56
Day	1	15	43	92	183	274	365	393
(±days)		(3)	(14)	(14)	(14)	(14)	(14)	(14)

\*A telephone contact (T) will occur between the scheduled Weeks 2 and 13 study visits (at approximately Week 6).

Note: The same 13-week visit schedule will be maintained for continued treatment beyond the first 12 months (if there is re-consent approximately every 12 months), with no requirement for the Week 2 visit in the second or any subsequent year of participation.

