### 7.3 Vital Signs

Vital sign measurements will be summarized descriptively by target visit using the visit windows defined in [Appendix A](#) and the last available on-treatment visit; baseline will be the last non-missing value prior to the first dose of study drug. The baseline data may come from the prior study, if not repeated in 020. Vital signs include seated blood pressure and pulse, temperature, respiratory rate, and body weight. Change from baseline will also be calculated and summarized. If a subject has multiple values within a visit window, the “worst” value as defined in [Appendix D](#) will be used for that visit window summary.

Potentially clinically significant vital sign changes are defined for selected parameters in [Appendix C](#). When there are thresholds provided for low and high values, they will be handled separately. Summaries will include the number and percent of subjects with treatment-emergent PCS values, restricted to those subjects in whom the values represent a post-baseline worsening (PCST). A PCST is defined as any PCS event that happened at any post-baseline visit and has a value more out of range than the value for a particular parameter at baseline (see [Appendix D](#) for directionality of worsening).

Listings of vital sign measurements including height at Screening will be presented. Listings will flag results that meet criteria as being PCS (whether or not a treatment emergent worsening).

Separate listings for each vital sign parameter will include only subjects with study-emergent PCS values and, for these subjects, all corresponding vital sign results will be provided.

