**Table 14.3.3.3.1**  
**Incidence of Potentially Clinically Significant Hematology and Serum Biochemistry Results**  
**Safety Population**

Laboratory Parameter	Potentially Clinically Significant Criteria	Target Visit	AD m/n (%)  (N= )	bvFTD m/n (%)  (N= )	All Subjects m/n (%)  (N= )
Hematology					
Hemoglobin	Criteria	Baseline	m/n (%)	m/n (%)	m/n (%)
		Any Post-Baseline PCS	m/n (%)	m/n (%)	m/n (%)
		Any Post-Baseline Worsening	m/n (%)	m/n (%)	m/n (%)
		Week 2	m/n (%)	m/n (%)	m/n (%)
		Week 13	m/n (%)	m/n (%)	m/n (%)
Serum Chemistry					
Sodium	Criteria	Baseline	m/n (%)	m/n (%)	m/n (%)
		Any Post-Baseline PCS	m/n (%)	m/n (%)	m/n (%)
		Any Post-Baseline Worsening	m/n (%)	m/n (%)	m/n (%)
		Week 2	m/n (%)	m/n (%)	m/n (%)
		Week 13	m/n (%)	m/n (%)	m/n (%)

Note: ULN = Upper Limit of Normal.

 m: number of subjects with at least one potentially clinically significant result at corresponding visit; n: number of subjects with at least one non-missing result at corresponding visit.

Note: For the post-Baseline visits, only subjects in whom the values represent a treatment-emergent worsening from Baseline (i.e. more out of range) are summarized.

path\t\_program.sas date time

*Programming note: Table will include all parameters with defined potentially clinically significant ranges at each post-Baseline visit and for Last Available On-Treatment Value. Please see Appendix A for target visits and visit windows. Ensure that criteria indicating an increase or a decrease are presented separately.*

*Programming Note: Repeat table for Table 14.3.3.3.2 Incidence of Potentially Clinically Significant Hematology and Serum Biochemistry Results – Non-AChEI/Memantine Users (Safety Population)*

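### The treatment-emergent PCS count pools new abnormalities with chance worsening in subjects already PCS at Baseline, and the planned tables do not separate them

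*SAP*

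**What the plan says.** Under SAP 7.2, a PCS result counts as PCST when it occurs after Baseline and "has a value more out of range than the value for a particular test at baseline". The section states no margin, confirmation or change of category. For the comparison, "Baseline is defined as the last non-missing value prior to first dose of study drug in 020", so one value is the reference. Subjects already PCS at Baseline are not excluded; the SAP says only that "the number meeting criteria at baseline will also be summarized".

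The shell for Table 14.3.3.3.1 (SAP Appendix G) has rows for *Baseline*, *Any Post-Baseline PCS*, *Any Post-Baseline Worsening* and each target visit. Its note says that at post-Baseline visits "only subjects in whom the values represent a treatment-emergent worsening from Baseline (i.e. more out of range) are summarized". The denominator is everyone with a result at that visit. No row is split by Baseline PCS status.

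SAP 7.3 applies the same rule to vital signs: a PCST value is one that "has a value more out of range than the value for a particular parameter at baseline". The columns are AD, bvFTD and All Subjects; there is no control.

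**The concern.** For a plain threshold, any value worse than a PCS Baseline is itself PCS. A subject already over the threshold therefore needs only one later value that is worse by any amount. Take a man with haemoglobin 11.4 g/dL at Baseline (the Appendix B limit for men is 11.5) and 11.3 g/dL at Week 26: he enters the treatment-emergent count on a change of 0.1 g/dL.

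Long-term safety is a primary objective, and the protocol names anaemia as a risk of the drug (4.7.8) and hemolytic anemia as an event of special interest (7.1.3). A reader of the table would want to know how many subjects developed a new abnormality on LMTM. The PCST row answers a different question, and no comparator column shows how much of it is background variation.

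**Working it through.** **Inputs from the documents**
- *Rule:* any later PCS value worse than one Baseline value, with no margin (SAP 7.2).
- *Number of later values, k:* SAP 3 says "post-Baseline study visits will occur at approximately 2 weeks (Visit 2), 13 weeks (Visit 3), 26 weeks (Visit 4), 39 weeks (Visit 5" and then Week 52, which makes 5 in year 1. Protocol 7.3 takes laboratory samples "after 2 weeks, and approximately every 13 weeks (relative to Baseline) thereafter (or upon early termination". SAP Appendix A has 9 on-treatment windows from Week 2 to Week 104. Unscheduled draws can add to k.
- *Criteria affected:* every Appendix B criterion except the haemoglobin decrease of at least 20%; in Appendix C only SBP ≤90 and DBP ≤50. The other vital-sign criteria require a change from Baseline, so they cannot be met at Baseline.

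**Assumptions (not in the documents)**
- No drug effect; normal values with a stable subject mean and independent noise.
- ICC r between 0.5 and 0.95; Baseline PCS prevalence q between 0.5% and 10%.

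The plan states no figure for this rule, so there is none to reproduce.

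**Step 1: simple upper guide.** Without selection on Baseline, the chance that at least one of k later values is worse than Baseline is k/(k+1): 5/6 = 83.3% and 9/10 = 90.0%. This is too high, because subjects picked for an extreme Baseline regress toward their mean.

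**Step 2: condition on a PCS Baseline.** On a unit-variance scale with the PCS cut-off at c = z(1−q):

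P = E[ 1 − Φ((b − m)/√(1 − r))^k | b > c ], with m given b distributed N(rb, r(1 − r)).

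**Step 3: share of the PCST count.** New crossings from a non-PCS Baseline, still with no drug effect, occur in a proportion

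I = E[ p − p^(k+1) ], with p = Φ((c − m)/√(1 − r)) and m distributed N(0, r).

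The share from Baseline-PCS subjects is qP/(qP + I).

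Example with q = 5%, r = 0.8, k = 5: P = 0.581, so qP = 0.05 × 0.581 = 0.0290. I = 0.0757. The PCST count is 0.0290 + 0.0757 = 0.1047, or 10.5% of subjects, and the share is 0.0290/0.1047 = 27.7%.

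**Results, k = 5 / k = 9**

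| q | quantity | r = 0.5 | r = 0.8 | r = 0.9 | r = 0.95 |
|---|---|---|---|---|---|
| 0.5% | P | 18.6 / 27.4% | 45.0 / 56.6% | 58.1 / 69.2% | 66.6 / 76.7% |
| | share | 4.6 / 4.2% | 16.3 / 14.5% | 27.8 / 24.9% | 39.9 / 36.6% |
| 2% | P | 28.8 / 40.1% | 52.5 / 64.2% | 63.1 / 73.7% | 69.8 / 79.5% |
| | share | 8.1 / 7.4% | 22.1 / 19.9% | 34.1 / 31.2% | 46.3 / 43.0% |
| 5% | P | 38.0 / 50.7% | 58.1 / 69.5% | 66.7 / 76.9% | 72.2 / 81.4% |
| | share | 12.3 / 11.4% | 27.7 / 25.4% | 40.0 / 37.1% | 51.8 / 48.6% |
| 10% | P | 46.6 / 59.7% | 62.8 / 73.8% | 69.7 / 79.5% | 74.1 / 83.0% |
| | share | 17.4 / 16.4% | 33.8 / 31.3% | 45.9 / 43.0% | 57.2 / 54.2% |

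Two cells checked by simulation agree (43.3% against 43.6% at q = 2%, r = 0.7, k = 5; 76.8% against 76.9% at q = 5%, r = 0.9, k = 9).

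**Step 4: when P passes one half.** With k = 5 the ICC must exceed 0.84, 0.77, 0.69 and 0.57 at q = 0.5%, 2%, 5% and 10%. With k = 9 the limits are 0.74, 0.63, 0.49 and 0.29.

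**Step 5: a single later value (early dropout, or one by-visit row).** P is 5–39% over the same grid, never a majority. The share does not vanish, though. For k = 1, I = q(1 − 2P), so the share is P/(1 − P). At q = 5% and r = 0.8, P = 0.248 and the share is 0.248/0.752 = 33%. The by-visit rows need the split as well.

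**The case against.** The strongest points on the other side are these.

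- *Size depends on assumptions.* ICC and prevalence are not in the documents. Several Appendix B limits are extreme (neutrophils ≤1.0 × 10⁹/L, platelets ≤75 × 10⁹/L, transaminases ≥3 × ULN), so prevalence may be low. Exclusion criterion 3 also lets the investigator keep out subjects with clinically significant abnormalities. This stands, and it rules out the tempting inference that most Baseline-PCS subjects will be counted by chance alone. That holds only for stable analytes or long follow-up. Exclusion 3 is a benefit–risk judgement, however, not a PCS cut-off, so such subjects can enrol.
- *The information is recoverable.* SAP 7.2 plans listings restricted to subjects with treatment-emergent PCS values, showing all their results, and the listing shell includes Baseline. The Baseline row also caps how many such subjects the PCST row can contain. Both are true, but the separation has to be done by hand. The protocol's low/normal/high shift tables (9.6.2), the nearest cross-tabulation by Baseline status, are not in the SAP's list of tables.
- *Worsening of an existing abnormality matters.* Protocol 9.6.2 asks both for subjects meeting criteria at Baseline and for treatment-emergent worsening. Baseline need not be drug-free: bvFTD subjects may enter on the day of their last dose in the prior study (Protocol 6.2.1). This stands. Worsening from a PCS Baseline must remain a reported category and must not be dropped.
- *A split does not remove chance.* In the worked example, 7.6 of the 10.5 percentage points are chance crossings from a non-PCS Baseline. This also stands.

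**Conclusion.** The definition has the stated property: it sets no minimum worsening, uses one Baseline value against 5 to 9 or more later ones, and keeps Baseline-PCS subjects in the count. Under the null model about 20–80% of those subjects enter the PCST count by chance, fewer with short follow-up, and they form roughly 5–55% of it (25–40% at 5% prevalence and ICC 0.8–0.9). Tied or rounded results would lower these figures; unscheduled draws would raise P.

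A reader might also infer that the vital-sign tables are affected throughout, or that a split would leave a clean drug-emergent rate. Neither follows. In vital signs the issue is confined to SBP ≤90 and DBP ≤50, and the haemoglobin decrease criterion is unaffected. In a single-arm study the new-PCS row keeps its own chance crossings. What is established is a reporting weakness with a cheap remedy, not evidence that the plan will misstate the drug's safety by a known amount.

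**What to change.** In SAP 7.2 and Tables 14.3.3.3.1 and 14.3.3.3.2, split *Any Post-Baseline Worsening* and the by-visit rows by Baseline PCS status:

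- (a) New PCS: numerator and percentage among subjects not PCS at Baseline who have a post-baseline value.
- (b) Worsening from a PCS Baseline: its own row, with the median and largest change from Baseline.

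In SAP 7.3 and Tables 14.3.4.1.3.1 and 14.3.4.1.3.2, apply the same split to SBP ≤90 and DBP ≤50 only, in the *Any Post-Baseline Visit* and by-visit rows (that shell has no worsening row). Add a footnote that row (a) includes chance crossings and has no control rate.

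No subject or result is lost, and all the data are already collected. The cost is SAP wording and a longer table.
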